1.5.1 Missing, unused and spurious data

The absence of any data will be carefully and critically considered. If appropriate, partial datasets will be included in the final analysis. Any data missing from a subject visit will be outlined in the report by indicating the number of subjects included for each analysis. Data that are unused or considered to be spurious will be detailed and discussed in the report.

1.5.2 Power analysis

Power analysis was conducted based on information from a previous study [REDACTED]

[REDACTED], assuming (a) that males vs. females are compared and (b) younger vs. older subjects are compared. For sex, power analysis based on previous data in spectacle wearers shows that for a two-sided two-sample t-test with an alpha of 0.05, assuming standard deviations of 0.95 for females and 2.61 for males, a sample size of 17 subjects in each group is required to detect a 2-hour difference in daily wearing time between groups with 80% power.

For age, power analysis on the same basis, assuming standard deviations of 3.31 for older subjects (> 10 years) and 0.68 for younger subjects (< 10 years), a sample size of 25 subjects in each group is required to detect a 2-hour difference in daily wearing time between groups with 80% power.

Given this, 60 subjects will be recruited to comprise approximately 50% males and 50% females, and with subjects recruited across the full age range. Subjects will be recruited into the following prescription range 'bins' (mean sphere) in approximately equal numbers; 1) plano to -1.50DS, 2) -1.75 to -3.75DS and 3) -4.00DS and above.

1.6 Risk analysis

This study is considered to be a non-significant risk study based on United States Food and Drug administration (FDA) and International Standards Organisation (ISO) guidelines due to the daily wear nature of the study. The work where practical will be conducted in accordance with:

- ICH Good Clinical Practice Guidelines
- BS EN ISO 14155 'Clinical investigation of medical devices for human subjects - Good clinical practice'
- Declaration of Helsinki

With the potential benefit of this study, the work is considered to be ethically justifiable. Ethical approval will be sought from the University of Manchester Senate Committee on the Ethics of Research on Human Beings (hereafter referred to as Manchester UREC).

1.7 Clinical trial registration

This study will be registered with clinicaltrials.gov in accordance with section 801 of the Food and Drug Administration (FDA) Act which mandates the registration of certain clinical trials of drugs and medical devices.

Section 2. Resources

2.1 Subject selection

In this work, up to 60 subjects will be recruited – approximately 15 at each of about four UK optometry practices. Note that the subjects will be recruited to comprise approximately 50% males and 50% females, and with subjects recruited across the age range 6-15 years. Subjects will be recruited into the following prescription range 'bins' (mean sphere) in approximately equal numbers; 1) plano to -1.50DS, 2) -1.75 to -3.75DS and 3) -4.00DS and above.

2.1.1 Subject accountability

This study includes an online information meeting where the subject and guardian or parent can ask questions and two clinic visits: one to fit the sensor and one to return the sensor. Once the study consent and assent forms are signed, the subject is considered to be enrolled on the study. All subject data will be included in the final analyses unless there are strong grounds for exclusion; such grounds will be detailed in the final report. If a subject withdraws after signing the consent form, they will not be replaced.

2.1.2 Subject recruitment

Subjects will be recruited directly from the patient bases at the optometry practices, using approved recruitment wording [REDACTED]

2.1.3 Inclusion criteria

Subjects will only be eligible for the study if:

1. They are aged between six and 15 years old.
2. Their parent or guardian understands the rights of the subject and are willing to sign a statement of informed consent.
3. They understand the study at a level appropriate for their age and are willing to sign a statement of assent.
4. They and their parents or guardians are willing and able to follow the protocol.
5. They currently use spectacle lenses for myopia control and have done so for at least three months.
6. They agree not to participate in other clinical research for the duration of this study.

2.1.4 Exclusion criteria

Subjects will not be eligible to take part in the study if:

1. They have an unusual ophthalmic history, which in the opinion of the site investigator or Principal Investigator might impact on the successful conduct of the study.
2. They are amblyopic.

2.2 Subject discontinuation

In general, subjects should be discontinued at any time, if it is in their best interests, as judged by the investigator. Reasons for this may include, lack of motivation, discomfort, repeated refusal to follow instructions or the use of non-study products. Subjects will be discontinued if a serious adverse event occurs or if they miss the study visit on two scheduled occasions. Subjects who fail to satisfy all the inclusion and exclusion criteria will be discontinued and replaced. Subjects may choose to leave the study at their own request. All discontinuations will be carefully recorded.

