1.4 Study design

This will be an unmasked multi-centre study which is controlled by cross-comparison. The wearing patterns of up to 60 established spectacle wearers will be evaluated via the use of temperature sensors fitted to the side of their spectacles. [REDACTED]

[REDACTED]

[REDACTED]. Subjects will wear the sensor for approximately one month. The data from the final week of this period will be used for analysis, in an attempt to minimise 'unusual' wear patterns which may occur early in the study as the subject adapts to being on a clinical study.

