2.5.1.1 Use of spectacles

Spectacles should be worn in line with normal wear patterns for the subject.

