3.1 Visit scheduling

Subjects will be required to attend an online information meeting followed by two clinic visits – an initial visit (Visit 1) and a follow-up visit (Visit 2), after approximately one month. Acceptable date ranges are shown in Table 2.

| Visit | Target | Allowable range |
|-------|----------------------|----------------------------|
| 1 | N/A | N/A |
| 2 | 28 days from Visit 1 | 20 to 40 days from Visit 1 |

Table 2: Visits and allowable ranges.

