3.1.2 Missed visits

Subjects not attending for a visit will be contacted and encouraged to return for assessment. If two scheduled appointments are missed, the subject will be discontinued. It is expected that study personnel at the optometry practices will attempt all reasonable means of communication in this event, including corresponding with the subject's parent/guardian by letter.

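### Does the lack of a stated rule for children without a complete final week put the age and sex comparisons at risk?

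*Combined protocol and SAP*

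**What the plan says.** - Section 1.4 fixes the analysis window: "The data from the final week of this period will be used for analysis". Section 3.1 sets Visit 2 at a target of 28 days, with an allowed range of "20 to 40 days from Visit 1".
- Section 2.2 is a best-interest rule. Its examples are "Reasons for this may include, lack of motivation, discomfort, repeated refusal to follow instructions or the use of non-study products", and it requires every discontinuation to be recorded. Section 3.1.2 adds: "If two scheduled appointments are missed, the subject will be discontinued".
- Section 1.5.1 covers incomplete data: "If appropriate, partial datasets will be included in the final analysis". It also promises the number of subjects in each analysis and an account of data that are unused or thought spurious.
- Section 2.1.1 sets the default: "All subject data will be included in the final analyses unless there are strong grounds for exclusion". Any such grounds must be set out in the final report. Children who withdraw after consent are not replaced.
- Section 2.5.1.1 gives the wear instruction: "Spectacles should be worn in line with normal wear patterns for the subject".
- Section 3.1 describes the contacts: "Subjects will be required to attend an online information meeting followed by two clinic visits".

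Parts of section 1.4 and all of section 3.2.1 are blacked out, so statements about what is absent concern the readable text only. Section 1.5.1 shows no redaction.

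**The concern.** Wearing time is the outcome, and the age comparison is the principal hypothesis (section 1.5). Lack of motivation, discomfort or refusal to follow instructions could all accompany low wear. If such children are stopped, withdraw or miss two appointments, they may have no final week, and the readable text names no substitute week and no minimum number of days. The conditions for using partial data or excluding a child are left to judgement once the data are in hand. Losses are recorded, but no breakdown by age group or sex is planned.

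Losing low wearers raises the mean of those who remain. The rise is proportional to the SD, so equal losses in two groups with very different SDs do not cancel. On the plan's own SDs, the older group's mean would rise more than the younger group's, and the male mean more than the female mean. A true deficit in older children could be hidden, or a difference could appear where there is none.

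**Working it through.** **Inputs.** Section 1.5.2 gives SDs of 3.31 h (older) and 0.68 h (younger), 0.95 h (female) and 2.61 h (male), a 2 h difference, two-sided alpha 0.05, 80% power and 60 subjects. Assumed here: 30 per group, normal wear times, Welch test. The documents give no loss rate.

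**The plan's own figures.** Standard error = √[(s₁² + s₂²)/n].
- Age, n = 25: √[(10.956 + 0.462)/25] = 0.676 h. Noncentrality 2/0.676 = 2.96, Satterthwaite df 26.0, power 81.3%.
- Sex, n = 17: √[(0.903 + 6.812)/17] = 0.674 h. Noncentrality 2.97, df 20.2, power 80.7%.

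The stated 25 and 17 per group are reproduced. At 30 per group, power is 88.1% (age) and 97.0% (sex). Sixty children against the 50 needed for age leaves room for 10 losses: at 25 and 25, power is still 81.3%.

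**Mild selection: k of 30 lost at random from the lower half of each group.** The mean of the lower half of a normal distribution lies 0.798 SD below the centre. The retained mean therefore rises by about 0.798k/(30 − k) SD. The contrast shifts by that factor times the SD gap, which for age is 3.31 − 0.68 = 2.63 h.
- k = 1: 0.798/29 × 2.63 = 0.07 h
- k = 2: 1.596/28 × 2.63 = 0.15 h
- k = 3: 2.394/27 × 2.63 = 0.23 h

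**Extreme selection: exactly the lowest fraction f lost in each group.** The mean rises by SD × φ(z_f)/(1 − f). At f = 10% the factor is 0.1755/0.9 = 0.195. Older: 0.65 h. Younger: 0.13 h. Shift: 0.51 h. Simulation with the lowest 3 of 30 removed gives 0.49 h.

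**Simulated results for age** (older minus younger; power is for a 2 h deficit in older children):

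| Loss per group | Shift (h) | Type I error | Power |
|---|---|---|---|
| None | 0 | 5% | 88% |
| 1, 3 or 6 at random | 0 | 5% | 87%, 84%, 80% |
| 1 from lower half | 0.07 | 5% | 85% |
| 2 from lower half | 0.15 | 5% | about 81% |
| 3 from lower half | 0.23 | 6% | 76% |
| 1 of the lowest 3 | 0.15 | 6% | 83% |
| Exactly the lowest 1 | 0.18 | 7% | 83% |
| Exactly the lowest 3 | 0.49 | 16% | 72% |
| Exactly the lowest 6 | 0.89 | 38% | 51% |

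For sex, 1 or 2 lost from the lower half gives shifts of 0.04 or 0.09 h and power of 96% or 95%. Losing exactly the lowest 1, 3 or 6 gives 0.12, 0.31 or 0.56 h, with type I error of 7%, 13% or 27%.

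**How a low wearer could be lost.** A child who habitually wears the spectacles little is following section 2.5.1.1, not refusing an instruction. Compliance is checked by questioning at study visits (section 3.3), and none is scheduled between fitting and Visit 2. Early loss therefore needs an unscheduled visit, a withdrawal or two missed appointments.

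**What happens to recorded data.** Under section 2.1.1 the data of a child who leaves early are included by default, and section 1.5.1 allows a partial set. The natural reading is the last recorded days. The plan already tolerates some variation in timing: the final week can begin about 13 days after fitting (20 − 7) or about 33 days after it (40 − 7).

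**Whether a fixed rule would do better.** A rule requiring the last seven complete recorded days would drop a child with five or six usable days, whom section 1.5.1 could keep. It recovers nothing when a sensor is not returned. A sensitivity analysis leaving out early stoppers would be a complete-case analysis, open to the same selection.

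**The case for a change.** The strongest case is that discretion exercised after the data are seen is what pre-specification is meant to remove, and a few sentences would remove it at almost no cost. The unequal SDs make this trial more sensitive than most to loss of low wearers. Even mild selection costs power: three children per group from the lower half takes age power to 76%, below the planned 80%, and six gives type I error of about 10%. Without losses broken down by age and sex, a reader could not judge whether they differed.

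Much of this stands as description. The readable text names no fallback week, and the simulated figures are sound. What does not stand is the step to a needed change. Nothing in the plan treats low wear as a reason to exclude a child, and excluding anyone has to be justified in the report. Losing six of 30 selectively in each group would be 20% attrition in a one-month observational study with two clinic visits, and nothing in the documents suggests it. Where the sensor data are lost altogether, no rule about which days to use alters the bias. Losses by age, sex and reason can be tabulated from the records that section 2.2 already requires.

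**Conclusion.** No change follows. The readable text leaves a small policy unwritten, and the inclusion default, the allowance for partial data and the reporting duties already steer analysts to a sensible choice. Under mild selection of 1 to 3 children per group, the age contrast moves by about 0.07 to 0.23 h, at most 12% of the 2 h target (0.23/2), and type I error stays at 5 to 6%. Power falls to between 85% and 76%. The 16% and 38% type I errors are upper bounds that require loss of exactly the lowest wearers in both groups.

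These sizes rest on an assumed 30/30 split, normal wear times, the plan's SDs and a two-group Welch test; section 1.5 allows regression instead. The true loss rate is unknown. If loss depended on absolute wear, the direction of any bias would also depend on the group means, which the readable text does not give. Confidence that no change is needed is moderate: it depends on early loss being uncommon, which the visit schedule makes likely but does not guarantee.

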2.3 Safety parameters, adverse events and concurrent illnesses

The key safety parameters are the serious and significant ocular adverse events listed in Appendix A (adverse events are classified as 'serious', 'significant' or 'non-significant'). Clinical assessment is made at the study visit(s) for these parameters. The presence of an ocular adverse event will be reported on the case report forms and those described as 'serious' or 'significant' will be detailed in the final report. Similarly, any concurrent illness that is likely to impact on the relevance and quality of the captured data will be noted on the case report form.

2.3.1 Investigator responsibilities

The investigators will be appropriately qualified, have suitable resources to conduct the study, have study training, ensure subject safety and data integrity. At all times they will act in the best interest of the subject. Referral or treatment of an adverse event or other clinical finding should be initiated in the best clinical judgement of the investigator, irrespective of their participation in the clinical study.

2.3.2 Investigator reporting responsibilities

In the case of a 'serious' or 'significant' adverse event, the Principal Investigator will notify the Sponsor as soon as possible. Manchester UREC and any regulatory authorities will be informed as required.

2.4 Study termination

If it becomes necessary to terminate the study earlier than planned, the Sponsor will notify the Principal Investigator who will end the study with the cooperation of other staff members. Manchester UREC will be informed.

2.5 Protocol deviations

These are unanticipated or unintentional changes that occur after Manchester UREC approval. Any deviations, major (affect the integrity of the study and/or subject safety) or minor from this protocol will be recorded, and reported to the Sponsor as appropriate. Manchester UREC will be informed as necessary.

2.5.1 Protocol amendments

Amendments will be agreed between the Sponsor and the Principal Investigator with the cooperation of other staff members. Amendments will be recorded, identified and distributed. Approval from Manchester UREC will be obtained as necessary.

2.5.1.1 Use of spectacles

Spectacles should be worn in line with normal wear patterns for the subject.

2.6 Study control

This study is controlled by cross-comparison.

2.7 Documentation

Documents related to this work that require archiving will be kept by Eurolens Research for a period of 20 years after completion of the final report. The Sponsor's permission will be sought before the documents are destroyed.

2.8 Data collection and analysis

Data collected in this work will be recorded on paper case report forms (CRFs), and Excel spreadsheets.

2.9 Study completion

The clinical phase of the study will be considered as complete when all subjects have attended their last visit.

2.10 Subject confidentiality

All matters related to this work will remain confidential within the optometry practices involved, Eurolens Research, the Sponsor and any regulatory authority (e.g. Manchester UREC). The relevant parties will take all reasonable steps to ensure that specific product information is not passed on to study subjects unless this is required for clinical management of an adverse event. Personal subject information will not be made available. To cater for this, subjects will only be referred by their unique identity number in the study report. The data activities of Eurolens Research are registered with the data protection officer at The University of Manchester.

2.11 Study monitoring

In order to provide quality control and quality assurance as part of this work, the study monitor will:

1. Liaise closely with the Principal Investigator.
2. Conduct site visits.
3. Monitor and ensure the safety of the subjects.
4. Ensure that the investigation is being conducted according to the protocol.

5. Monitor and review (or oversee review of) the study records to ensure accuracy.
6. Review study product accountability.
7. Document their observations and make them available to relevant authorised parties (e.g. Manchester UREC).
8. Implement the Eurolens Research clinical monitoring standard operating procedure.

Section 3. Subject management

3.1 Visit scheduling

Subjects will be required to attend an online information meeting followed by two clinic visits – an initial visit (Visit 1) and a follow-up visit (Visit 2), after approximately one month. Acceptable date ranges are shown in Table 2.

| Visit | Target | Allowable range |
|-------|----------------------|----------------------------|
| 1 | N/A | N/A |
| 2 | 28 days from Visit 1 | 20 to 40 days from Visit 1 |

Table 2: Visits and allowable ranges.

3.1.1 Unscheduled visits

An unscheduled visit is an interim visit requested by the subject or investigator due to an unanticipated event. Pertinent data will be collected and will be recorded on the CRF.

3.1.2 Missed visits

Subjects not attending for a visit will be contacted and encouraged to return for assessment. If two scheduled appointments are missed, the subject will be discontinued. It is expected that study personnel at the optometry practices will attempt all reasonable means of communication in this event, including corresponding with the subject's parent/guardian by letter.

3.2 Visit conduct

3.2.1

A series of horizontal black bars of varying lengths, likely representing redacted text or data. The bars are arranged in a grid-like pattern, with some bars being significantly longer than others, creating a visual representation of data that has been obscured.

3.2.2 Informed consent

The subject's parent/guardian will be required to sign an informed consent form, and the subject sign an assent form, prior to enrolment [REDACTED] and before any procedures

specific to the clinical investigation are performed. A copy of the signed forms will be issued to the subject and their parent/guardian. They are then considered to be enrolled on the study.

3.2.3 Visit 1

Subjects should attend wearing their spectacles. Written assent/consent from the subject and parent/guardian will be obtained as detailed in section 3.2.2.

The following procedures will be performed:

1. The temperature sensor will be fitted to the spectacle frame (or a side with sensor fitted). The frame will be fitted to the face to ensure that the sensor is in comfortable contact with the skin.
2. The subject will be discharged from this clinic visit, and asked to return four weeks later.

3.2.4 Visit 2

Subjects should attend wearing their spectacles. The following procedures will be performed:

1. The temperature sensor will be removed from the spectacle frame (or the old side refitted).
2. Study payment will be issued/processed, and the subject will be discharged from the study.

3.2.5 Post-study follow-up visit

In the case of a subject who exits the study with significant clinical signs or symptoms, the investigator must undertake to examine the subject at intervals they determine to be clinically appropriate until the sign or symptom has resolved or returned to a level that is considered to be clinically acceptable. Details from these visits will be recorded on a post-study follow-up visit form.

3.3 Monitoring subject compliance

Subjects are required to adhere to the instructions provided during this clinical investigation. This will be confirmed at the study visit(s) by verbal questioning of the subject and parent/guardian by the investigator.

Section 4. Study co-ordination

4.1 Document processing

All case report forms will be processed and evaluated by Eurolens Research, who will produce the final report with full statistical analysis. A draft report will be sent to the Sponsor in order to make comments and ask for re-drafts. If no comments are received from the Sponsor within eight weeks, a final report will be released with a separate document control page, requesting the Sponsor to sign and return to Eurolens Research.

